## 5.2 Recruitment Methods

Long-COVID Patients will be recruited through recruitment from James J. Peters VAMC Long-COVID clinical program and clinician referrals. The Bronx had significantly higher rates of COVID-19 infection than other boroughs in New York City. Thus, recruitment of *up to 36 Veterans* is feasible within the 18-month timeframe.

**Limitations and Future Directions.** One potential issue may be the recruitment of Veterans with Long-COVID. However, a strength of the proposed study is it's involving telehealth, making it more appealing to participants and less prone to no-shows. We will also recruit from our in-house Long-COVID center and multiple existing national Long-COVID programs. While the JJPVAMC is diverse in race and ethnicity, our

study may still have a diversity limitation as it will be conducted in an urban northeast VAMC and may not fully generalize to other areas of the USA. Future studies should extend the findings across other VAMCs. During year 2 we will submit a Merit Award to complete the planned follow up study testing the final manualized version of LC-CR (developed in this SPiRE project) in a multi-site clinical efficacy RCT.

Veteran participants will be offered financial compensation for their participation based on completion levels of the following:

Research Procedure for LC-CR	Participant Compensation
Pre-Treatment Baseline Assessment	\$75
Post-Intervention Assessment (Mod 1)	\$75
Post-Intervention Assessment (Mod 2)	\$75
Post-Intervention Qualitative Interview (Mod 2).	\$75

You will also receive a \$50 bonus upon completion of each therapy module (after the first 8 sessions and after the second 8 sessions).

Participants who consent to enroll in the EMA portion of the research study will be compensated for their participation. The JJPVAMC will be responsible for compensating patients. Participants will be compensated per survey initiated (i.e., at least one question is answered). Participants can receive up to \$135 across all three week-long bursts of daily surveys.

At this time, we anticipate providing a maximum of \$135 per person for participating. Each burst listed below lasts for 7 days. The payment schedule is as follows:

- Burst 1, baseline: \$4 per daily assessment initiated
  - Maximum: \$28 for this burst
- Burst 2, mid-treatment: \$5 per daily assessment initiated
  - Maximum: \$35 for this burst
- Burst 3, end of treatment: \$6 per daily assessment initiated
  - Maximum: \$42 for this burst
- In addition, we will offer an extra \$10 incentive for initiating 5 or more daily assessments per burst.
- Thus, total possible is \$135 per person, including all \$10 bonuses.

Note: initiation means filling in at least 1 question on the survey (out of approximately 20).

### 5.3 Informed Consent Procedures

Veterans will be recruited from the Post-COVID Clinic and other medical providers at the JJPVAMC.

Prior to participation in the protocols, patients are called by research personnel at which time the nature of our program, the procedures involved, and alternatives to the study are discussed. The patient must understand and be able to articulate the risks and benefits of the research protocols and understand the alternatives. Patients who agree to participate are reimbursed for their time and inconvenience at rates that do not represent inducement. After the protocol is described to the subject and the subject's questions are answered, the subject will be asked to summarize the procedures that he/she will undergo and to describe 2 risks involved in the study. If there is any doubt about the subject's capacity to give consent, an independent psychiatrist will assess the subject to determine whether they understand the study and can give informed consent.

Consent will be obtained upon talking with the Veteran if s/he agrees to participate in the study (over the phone at this time if it is unsafe to consent in person). The individuals communicating information to the participant during the consent process will provide that information in language understandable to the participant.

The information being communicated to the participant during the consent process will not include exculpatory language through which the participant is made to waive or appear to waive any of the participant's legal rights. When the investigator verbally obtains consent, the participant will not be made to feel as if he or she has waived any of his or her rights as a human subject. The main purposes of the consenting process are for the investigator to inform the participant in detail about what will take place during the study, to allow the participant to ask any questions that he or she may have, and to explain to the participant that he or she is a volunteer for the study and may choose to decide against taking part at any point in time.

We ensure that the information being communicated to the participant during the consent process will not include exculpatory language through which the investigator, the sponsor, the institution, or its agents are released from liability by providing patients with contact information for the PIs and co-investigators should they feel that they have suffered an injury. Furthermore, patients are informed in the consent document that if they are eligible veterans, they are entitled to medical care and treatment if they experience any adverse effects resulting from the study. Participants are also provided with the contact information for the JJP VA IRB should they have questions regarding the research or their rights.

The informed consent form includes information related to the procedures, risks, and benefits of the optional EMA study. Those participants who consent to the optional EMA study will be given an Information Sheet with additional information about the EMA study, its risks and benefits, and assessment and compensation plan.

## **5.4 Inclusion/Exclusion Criteria**

Inclusion criteria include: (1) U.S. Veteran (2) Age 18-80 (3) Screened positive for Long-COVID (e.g., COVID-19 positive, diagnosed with a PCR test and/or an antibodies blood test, and symptoms lasting 1 month or longer after infection (4) Participation in VA Services the JJPVA (5) Sufficient clinical stability and readiness to participate in a group therapy as deemed by their VA Service provider,

Exclusion criteria include: (1) Active alcohol or opiate dependence requiring medically supervised withdrawal. (2) Active psychosis. (3) MINI Mental Status < 23 or inability to function in a group setting. (4) Those unable to operate telehealth platforms or other devices. (5) Unable to speak English. (6) Lack of capacity to consent. (7) Unable or unwilling to provide at least one contact for emergency purposes.

## **5.5 Study Evaluations**

**Clinical Assessments and Schedule.** Patients will have been screened/diagnosed as a part of their local VAMC's Long-COVID Clinical Center. Interested eligible participants will enroll and undergo assessments at pre (consent & baseline), immediately post module 1 of therapy (after first 8 sessions) and immediately post module 2 of therapy (after second 8 sessions) via either in person, over the phone, or via HIPAA-compliant web platform VA Video Connect (VVC) (with Audacity audio recording software) with VA WebEx as a viable backup depending on the participant's preference/availability.

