## 5.0 Study Procedures

## 5.1 Study Design

**Group Intervention.** Veterans will participate in a LC-CR group (75 minutes 1x/week for a total of 16 sessions) via the HIPAA-compliant telehealth platform VA Video Connect (VVC) in accordance with the Office of Connected Care (OCC)'s best telehealth practices. VA WebEx will be available as an approved back-up telehealth platform in the event of VVC technical difficulties.

The intervention will be delivered in two modules consisting of 8 sessions each (16 sessions total):

**Module 1:** The first 8 sessions of the treatment will focus on skill based coping strategies to target more immediate symptoms and Long-COVID related issues as part of the recovery process.

**Module 2:** The second 8 sessions will focus on more long-term recovery and creating a meaningful and purposeful future.

Sessions will be co-facilitated by [name] and another co-therapist. [name] will be the co-therapist for Module 1 of therapy (first 8 sessions) and [name] will be the co-therapist for Module 2 of therapy (second 8 sessions).

**Timeline:** (See **GANTT chart**) For the first 3 months we will complete the needs assessment interviews. In months 4-7, we will revise the psychotherapy workbook and therapist manual *and will consult with stakeholders monthly for input on revisions throughout our piloting phases*. In months 18-24, we will develop and submit a RR&D Merit grant application for an RCT to test the treatment.

Project dates: 10/1/22- 9/30/24	Year 1				Year 2			
	Q1	Q2	Q3	Q4	Q1	Q2	Q3	Q4
Activity	October - December (2022)	January-March (2023)	April-June (2023)	July-September (2023)	October-December (2023)	January-March (2024)	April-June (2024)	July-September (2024)
IRB								
Train RA and other startup activities								
Complete PACS needs assessment								
Analyze needs assessment results								
Finish developing psychotherapy materials and therapist manual								
Consult with stakeholders on proposed intervention and revise materials								
Run first set of pilot group								
Revise treatment based on trial participants and stakeholder feedback								
Run second set of pilot groups								
Present findings								
manuscript preparation								
Merit preparation/sSubmission								

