MINI Mental State Examination (MMSE)	Cognitive Function	Consent & baseline	1
The World Health Organization Disability Assessment Schedule, 2nd Version (WHODAS 2.0)	Functional Status as relates to health (primary outcome)	Consent & baseline, post- Mod 1, Post Mod 2,	3
Suicide Behaviors Questionnaire- Revised (SBQ-R)	Suicidal Risk/Behavior	Consent & baseline, post- Mod 1, Post Mod 2,	3
Measure of Current Status (MOCS)	Resilience	Consent & baseline, post- Mod 1, Post Mod 2,	3
The Quality of Life Scale (QOLS)	Quality of Life	Consent & baseline, post- Mod 1, Post Mod 2,	3
Future Self-Continuity Questionnaire, (FSCQ)	Identity Concerns	Consent & baseline, post- Mod 1, Post Mod 2,	3
GAD-7 Anxiety	Anxiety	Consent & baseline, post- Mod 1, Post Mod 2,	3
Patient Health Questionnaire- 9 (PHQ-9)	Depression	Consent & baseline, post- Mod 1, Post Mod 2,	3
COVID-19 Yorkshire Rehabilitation Scale (C19-YRS)	Long COVID Symptom severity	Consent & baseline, post- Mod 1, Post Mod 2,	3
Questionnaire about the Process of Recovery (QPR)	Progress through Recovery Process	Consent & baseline, post- Mod 1, Post Mod 2,	3

**Feasibility and acceptability metrics.** Feasibility will be tracked through 1) implementation ease - tracking the hours clinicians spend in preparation, delivery, and supervision with a target of 100 hours/ cycle (5 hours per group). 2) recruitment - tracking referrals and 3) attendance/retention - tracking the sessions Veterans attend. Our criteria for retention will be “adequate” if 60% attend at least 5 of the first 8 sessions (Module 1), 5 of the second 8 sessions (Module 2), and 10 of the total 16 sessions (Module 1 + Module 2). A similar strategy will be used for recruitment rates, with feasibility deemed “adequate” if at least 60% of Veterans approached for participation in the study agree. At the end of each session, we will ask veterans the following questions: “What did you like about this session?” “What did you not like about this session?” “Do you have any suggestions for improvement?” to gauge acceptability, feasibility, and appropriateness of each session.

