Veterans will complete the AIM, IAM and FIM ( Weiner et al., 2017) prior to and after completion of the program. These are four-item measures of implementation outcomes (acceptability and feasibility of intervention and intervention appropriateness) that are often considered “leading indicators” of implementation success (Proctor et al., 2011). We will also track homework adherence by percent complete. Lastly, upon completion of all LCCR sessions we will ask the veterans’ additional questions to obtain *participants’ feedback on the group*. Responses will be de-identified and analyzed for future development and implementation purposes.

Test /Procedure:	Outcome	When:	# of times:
Acceptability of Intervention Measure (AIM) Weiner et al., 2017)	How acceptable or satisfactory is the LC-CR group is to Veterans	Pre-treatment, Post-treatment (Mod 1), Post treatment (Mod 2)	3
Intervention Appropriateness Measure (IAM) Weiner et al., 2017)	How is the perceived fit, relevance, or compatibility of LC-CR to Veterans	Pre-treatment, Post-treatment (Mod 1), Post treatment (Mod 2)	3
Feasibility of Intervention Measure (FIM) Weiner et al., 2017)	How easy is it to participate in LC-CR	Pre-treatment, Post-treatment (Mod 1), Post treatment (Mod 2)	3
Qualitative Interviews	Acceptability, Feasibility, and Appropriateness of Intervention to help identify other needed implementation strategies for future dissemination	Post-treatment (Mod 2)	1

**5.5.1 EMA Protocol (to be carried out at Minneapolis VA by [name] team):** Participants who opt-in to the optional EMA component of the study during the consent process will be scheduled to receive three different week-long bursts of daily surveys (one at baseline, mid-treatment, and end of treatment). Each survey will contain approximately 20 questions and will be delivered at the end of the day (at a personalized time). They are expected to take approximately 3 minutes to complete. The surveys do not contain any intervention component. Participants will receive links to these questionnaires via text message.

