## **8.0 Communication Plan**

All risks and potential complications are discussed with the subjects during consent signing, and any new information regarding risks will be provided by phone immediately. Patients are monitored closely and should any unanticipated findings arise, the IRB will be notified. Supervision and weekly consultation team meetings will provide a forum for study staff/clinicians to review results of ongoing safety monitoring. During this meeting, any concerning results will be discussed, troubleshooted, and a plan of action will be developed (e.g., decisions about referrals to outside treatment services, termination of subject participation. The PI will work in conjunction with the IRB to evaluate any emerging information and determine if and how the study should be continued.

Chart reviews will be conducted during recruitment of each cohort to ascertain which/if participants have an assigned mental health care provider and safety plan (if they have history of suicidal behavior).

Safety monitoring for adverse events (AEs) will be conducted in real time by the Principal Investigators and the research coordinators. The PI will supervise the research and respond directly to patient problems. In the case of AEs, all of them will be indicated on the source documentation for the specific adverse event report form. The PI will determine the severity of the event, will assign attribution to the event, and will monitor the event until its resolution.

Additionally, the PI [name] (licensed psychiatrist), and co-Is [name] (licensed psychologist) and [name] (licensed psychologist), and therapy facilitator [name] (licensed psychologist)

will be available to evaluate through mental health assessments if at any point a participant is displaying psychological distress and subsequent behavior. They and other research staff will be able to alert the participants' primary mental health provider through CPRS in case additional support is needed.

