**Developing an Integrative, Recovery Based, Post-Acute COVID-19 Syndrome (PACS)
Psychotherapeutic Intervention, “PACS Coping and Recovery”**

Funding Agency: Rehabilitation Research and Development Service (RR&D) Small Projects in Rehabilitation Research (SPiRE).

NCT05453201

June 1, 2024

JJPVAMC

PI: [name]

Co-I: [name]

Co-I: [name]

Co-I: [name]

All statistical analyses were conducted using the RStudio (version 4.4.2). Item-level missingness (< 0.5% item-level observations) was handled with participant-mean imputation. Little's (1988) missing completely at random (MCAR) test was not significant ($p > .05$) indicating that the data were missing at random. Paired-sample t-tests were used to examine changes in primary and secondary outcomes from pre- to post-treatment. Paired Wilcoxon tests were used when the Shapiro-Wilk test was significant ($p < .05$). The significance level was set at $p < .05$ for all analyses.

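### Nothing ties the pre assessment to session 1, so pre-post change on the nine repeated scales, including the primary WHODAS 2.0, can include time before LC-CR began

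*Protocol*

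**What the plan says.** Protocol 5.5 sets the first assessment as follows: "Interested eligible participants will enroll and undergo assessments at pre (consent & baseline), immediately post module 1 of therapy". The third comes directly after Module 2.

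The schedule table in 5.5 lists nine scales given three times: WHODAS 2.0, SBQ-R, MOCS, QOLS, FSCQ, GAD-7, PHQ-9, C19-YRS and QPR. The first occasion for each is labelled as consent and baseline. The WHODAS 2.0 row reads "Functional Status as relates to health (primary outcome". The MMSE, an eligibility screen given once, carries the same label.

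The first visit has other names elsewhere. The compensation table in 5.2 calls it "Pre-Treatment Baseline Assessment", and the AIM, IAM and FIM are timed as "Pre-treatment, Post-treatment (Mod 1), Post treatment (Mod 2".

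On delivery, 5.1 describes 16 weekly group sessions in two modules taken in order. The timeline there lists a first set of pilot groups, a revision of the treatment, and then "Run second set of pilot groups". Section 8.0 adds: "Chart reviews will be conducted during recruitment of each cohort". Section 5.2 gives the target: "recruitment of *up to 36 Veterans* is feasible within the 18-month timeframe".

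On analysis, the SAP says: "Paired-sample t-tests were used to examine changes in primary and secondary outcomes from pre- to post-treatment". Protocol 5.6 names repeated-measures mixed models across the time points. Neither document describes a comparison group.

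**The concern.** The two ends of the pre-post interval are fixed to different things. The later assessments are fixed to therapy; the first is fixed to enrolment. Veterans consent one by one (5.3), but a group starts on one date for all its members. Members of the same group may therefore have different intervals between their pre value and session 1, and the plan puts no limit on them.

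With no control arm, any change in that interval is counted as change under LC-CR. Aim 2 is to identify possible benefits of LC-CR and Aim 3 is to inform a large RCT, so the pre-post change on WHODAS 2.0 is likely to be read as a first signal. A drift before session 1 could create such a signal or hide one.

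**Working it through.** The documents give no interval from baseline to session 1, no group size and no rule for starting a group, so there is no stated figure to reproduce. The check has two parts.

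**What the text fixes.** The first assessment belongs to enrolment (5.5, text and table). Any of the C19-YRS, PHQ-9 and GAD-7 that is missing from the chart or too old is done by study staff after consent (5.5). No section sets a maximum interval to session 1, a repeat baseline, or an analysis that uses the interval. The pre-treatment labels in 5.2 and 5.5 require only that the visit comes before treatment, which is true one day or several months before session 1.

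**How large the wait could be (illustration).** Inputs:

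- Treatment: 16 weekly sessions (5.1), so 16 × 7 / 30.44 = 3.68 months.
- Accrual: 36 Veterans / 18 months = 2 per month (5.2). A rate of 4 per month is an assumed faster case.
- Group size m: assumed 6 or 9.
- Start rule: assumed, with even accrual and the group starting when its last member enrols.

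Mean wait = (m − 1) / (2 × rate). Longest wait = (m − 1) / rate. Share of the pre to post-Module 2 interval = mean wait / (mean wait + 3.68).

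| Rate per month | m | Mean wait (months) | Longest wait (months) | Share at mean wait |
|---|---|---|---|---|
| 2 | 6 | 5/4 = 1.25 | 2.5 | 1.25/4.93 = 25% |
| 2 | 9 | 8/4 = 2.00 | 4.0 | 2.00/5.68 = 35% |
| 4 | 6 | 5/8 = 0.625 | 1.25 | 0.625/4.305 = 15% |
| 4 | 9 | 8/8 = 1.00 | 2.0 | 1.00/4.68 = 21% |

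If baseline is booked just before session 1, or recruitment comes in a burst, the wait and the share are close to 0.

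**What drift would do to the test.** Let d be the mean drift before session 1 in SDs of the change score, with no LC-CR effect. By the normal approximation, a two-sided 0.05 paired test (sidedness is not stated) rejects with probability 1 − Φ(1.96 − d√n) + Φ(−1.96 − d√n). At n = 36, d of 0.1, 0.2 and 0.3 gives d√n of 0.6, 1.2 and 1.8, and rejection rates of about 9%, 22% and 44%. At n = 12 the rates are about 6%, 11% and 18%. These values of d are assumptions; the documents give none.

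**A separate rule that adds to this.** For C19-YRS, PHQ-9 and GAD-7, 5.5 allows a chart value up to 3 months before enrolment. That alone could be 3/(3 + 3.68) = 45% of the interval, and any wait after enrolment comes on top. WHODAS 2.0 is not part of that rule.

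**The case against.** The strongest reply is that the documents do not show a wait at all. The consent and baseline label names two things and need not put both on one day. The visit is elsewhere called pre-treatment, and a site could already book it close to session 1. This stands as to length: the wait is permitted, not demonstrated. It does not remove the gap, because nothing in the plan makes a site book the visit that way.

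A reader might infer that groups are closed and start only once a cohort is complete. The ordered modules, the two sets of groups and the mention of cohorts make that plausible, but neither document says it, and group size is not given. A reader might also infer very long waits by supposing that 18 Veterans are recruited at 2 per month before any group starts (17/2 = 8.5 months for the first). Nothing supports that scenario. Accrual may well be faster: the workbook and manual are revised in months 4 to 7 (5.1), and if enrolment followed, 2 per month would reach 36 at month 7 + 18 = 25, beyond the 24-month project. The timeline bars could not be read in the text available and might narrow the range.

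It is also fair to say that the overall goal is acceptability and feasibility, that efficacy is left to a later RCT, and that a better baseline would not make an uncontrolled comparison causal. This limits the importance of the point, but the gap remains an avoidable source of error in the analysis that the SAP does specify.

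**Conclusion.** The point holds in limited form and should be acted on. For the nine repeated scales, including the primary WHODAS 2.0, the pre value is tied to enrolment, delivery is by group, and no window or repeat baseline links that value to session 1. The uncontrolled pre-post tests can therefore include a period before LC-CR that varies between Veterans.

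Its length is not established. The 0.6 to 2 months (15% to 35% of the interval) rests on assumed group sizes, even accrual at 2 to 4 per month and a start when full; near zero is also compatible with the text.

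Four wider readings are not supported:

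- Every scale is affected. The MMSE is given once and has no change score, and the AIM, IAM and FIM are labelled pre-treatment.
- Every Veteran waits. Even in the illustration, the last to enrol does not.
- The period is untreated. It is only without LC-CR, which Protocol 2.0 presents as an addition to other care.
- The direction of bias is known. The follow-up study cited in 3A found anxiety or depression rising between 6 and 12 months in hospitalized patients. That shows worsening only, in one subgroup, and says nothing about WHODAS 2.0. Worsening before session 1 would make LC-CR look less helpful.

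The change from post-Module 1 to post-Module 2 is not affected.

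**What to change.** Keep consent and the MMSE at enrolment. In 5.5, schedule WHODAS 2.0 and the other repeated scales within a stated short window before session 1 of the Veteran's group. Fourteen days is a reasonable choice, but it is ours and not from the documents; it would cap the period before LC-CR at 2/(2 + 16) weeks = 11% of the interval. Repeat the scales if the window is exceeded, define the value closest to session 1 as pre in the SAP, and record both dates. The chart rule for C19-YRS, PHQ-9 and GAD-7 counts back from enrolment and would need to be aligned with this window.

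The SAP is in the past tense and reports missing-data results, so the data may already be collected and a repeat baseline no longer possible. In that case, report the distribution of the interval from baseline to session 1, add a sensitivity analysis restricted to short intervals or adjusted for the interval, describe the result as change since enrolment, and set the window for the planned RCT.

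The cost is a few lines in 5.5 and the SAP, and a repeat of short questionnaires for some early enrollees. There is no extra assessment of the staff-administered scales where the visit is booked once the start date is known. The change does not remove natural course or regression to the mean during the 16 weeks of treatment.
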